**Table 3: Hydroxychloroquine and Entinostat Phase I: Dose Escalation Schema**

Dose Level	Dose Hydroxychloroquine (mg/day)	Schedule of HCQ Administration	Dose Entinostat
-1	400 mg	200 mg q12h	2 mg weekly
1	600 mg	200 mg qAM/ 400 mg qPM	3 mg weekly
2	600 mg	200 mg qAM/ 400 mg qPM	5 mg weekly
2A	800 mg	400mg qAM/400mg qPM	5 mg weekly
2B	1000 mg	400mg qAM/600mg qPM	5 mg weekly
3	1200 mg	600 mg q12h	5 mg weekly

Tablets of HCQ are available in 200 mg strengths. HCQ will be administered in two divided doses daily. When taking HCQ twice daily, the two daily doses should be taken as close as possible to 12 hours apart. Patients will be instructed to swallow the whole tablet in rapid succession without chewing. Patients receiving antacids, sucralfate, cholestyramine, and/or bicarbonate should have the HCQ and entinostat drug doses administered at least 1 hour before or 2 hours after these medications.

### ***4.3 Phase II Dose Expansion***

To determine the recommended phase II dose (RP2D), at least 6 patients must be treated at the MTD for 2 cycles. In order to fulfill this criterion, patients who go off study before the completion of 2 cycles for reasons other than toxicity (e.g. disease progression) will be replaced in this cohort. The RP2D will be defined as a dose in which fewer than 33% of patients have a DLT and at which chronic administration is tolerated. To evaluate for chronic toxicity, tolerability is defined as 4 out of 6 patients treated for 2 cycles at the RP2D receiving during cycle 2:

- 1) At least 80% (in total mg per cycle) of the regorafenib dose at which the patient begins cycle 2
- 2) At least 75% of entinostat doses, with no more than one dose reduction
- 3) At least 80% (in total mg per cycle) of the HCQ doses

Should chronic tolerability fail to be demonstrated at the initial RP2D, the previous dose level (or a lower dose level at the discretion of the principal investigator) will be expanded until at least 6 patients have been treated at this new RP2D for 2 cycles. Evaluation for chronic tolerability will be performed as above after 2 cycles until the RP2D is determined.

After determination of the RP2D, an additional 20 patients will be enrolled at this dose level in the Phase II portion.

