## 7.0 STATISTICS

### 7.1 Primary Endpoints

#### 7.1.1 Phase I

The Phase I methodology will be a standard Phase I escalating trial with three patients per level, expanding to six patients per level in the event of dose-limiting toxicity at any level, and provision for expansion to 20 additional patients at the recommended Phase II dose to better characterize the optimal dose and the variation in toxicity at that level. A minimum of 4 weeks of combination therapy with hydroxychloroquine, entinostat, and regorafenib are required in the third patient before escalation to the next dose is initiated. At the MTD, at least 6 patients must be treated for 2 cycles to evaluate chronic toxicity and determine the RP2D (see section 4.3 for details).

We will calculate the percentage of subjects with toxicities at each dose level. We expect that doses close to full single agent doses will be tolerable. Three patients will be initially treated at each dose level. The plan for escalation is described below:

Three patients will initially be treated at each dose level.

If 0/3 patients experience DLT, then the dose will be escalated.

If 2-3/3 patients experience DLT, then the MTD has been exceeded. Three additional patients are treated at the previous dose (if only 3 had been treated) as a total of 6 patients must be treated at the MTD.

If 1/3 patients experience DLT, then 3 additional patients are treated. If none of the additional patients develop DLT, then the dose will be escalated, otherwise escalation ceases and the previous dose will be expanded to a total of 6 patients.

To assure safety in this phase I study, the operating characteristics of the escalation rule to be employed have been determined. The operating characteristics denote the probability of escalation to the next dose level, for a given true DLT rate. For a true DLT that is high, we desire the probability of escalation to be low. As noted in the table, the probability of escalating beyond a certain dose level, if that dose level truly has a 10% DLT rate, is 0.91. On the other hand, if the true DLT rate is 40%, there is only a 31% chance of dose escalation.

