### 7.1.2 Phase II

Single agent regorafenib showed ORR of 1% in phase III trials in advanced colorectal cancers. We anticipate being able to improve this response rate substantially, perhaps to 15% or more. We will enroll a total 26 patients at the RP2D, including those treated during the phase I portion of the study. Sample size calculations are based on an assumption of at least 20 evaluable patients. With 20 patients, an exact binomial test with a 0.05 one-sided significance level will have 84% power to detect an improvement from the historical rate (null hypothesis proportion) of 1% to an improved rate (alternative proportion) of 15%.

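### The RP2D is judged on as few as six patients, and no rule in the available text lets DLTs in the 20 added patients pause enrolment or reopen that judgement

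*Combined protocol and SAP*

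**What the plan says.** Section 4.3 requires that "at least 6 patients must be treated at the MTD for 2 cycles" before the RP2D is set. It gives two criteria. The first is toxicity: "The RP2D will be defined as a dose in which fewer than 33% of patients have a DLT". The second is chronic tolerability: "tolerability is defined as 4 out of 6 patients treated for 2 cycles at the RP2D" must receive stated fractions of each drug during cycle 2. If tolerability fails, a lower level is expanded and re-evaluated. The section ends with the expansion: "After determination of the RP2D, an additional 20 patients will be enrolled at this dose level in the Phase II portion".

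Section 7.1.2 gives the total: "We will enroll a total 26 patients at the RP2D, including those treated during the phase I portion of the study". Section 7.1.1 states what the 20 extra patients are for: "to better characterize the optimal dose and the variation in toxicity at that level".

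The DLT decision rules are in sections 4.2, 4.5 (with Table 4) and 7.1.1. They deal with Phase I cohorts of three and six. Section 7.2 plans toxicity rates with 95% confidence intervals, without a threshold or an action. Section 7.3 speaks of up to 20 further patients, with no criterion for taking fewer.

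**The concern.** Of the 26 patients planned at the RP2D, 20 supply their toxicity data after the dose has been chosen. The plan names better knowledge of toxicity as a purpose of the expansion but does not say what would follow if that knowledge were unfavourable. The only fallback to a lower level in section 4.3 is triggered by failed chronic tolerability, before the 20 are enrolled.

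Two things are at stake. Patients could go on being enrolled at a dose whose accumulated DLT rate exceeds the plan's limit. The trial could also report as its RP2D a dose that does not meet its own definition of one. The background section describes pairs of these or related drugs but no data on all three together, and section 4.2 itself mentions possible overlapping toxicity. The early estimate therefore has little outside support.

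**Working it through.** **Inputs.** At least 6 patients for the RP2D, DLT limit below 33%, 20 added (section 4.3); 26 in total (section 7.1.2); DLT window of 4 weeks, not restricted to Phase I (section 4.5). I take exactly 6 patients at the first judgement and a constant true DLT rate p.

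**1. The plan's own figures.** The escalation probability is (1−p)³ + 3p(1−p)²·(1−p)³. At p = 0.4 this is 0.216 + 0.093 = 0.309, against 0.31 in Table 11; all eight entries reproduce. The 88% in section 7.2 also reproduces: 1 − 0.9²⁰ = 0.878. The Phase I arithmetic is sound.

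**2. What the limit means in counts.** 2/6 = 33.3% fails, so at most 1 of 6 passes. 8/26 = 30.8% passes; 9/26 = 34.6% fails.

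**3. What six patients show.** Exact (Clopper-Pearson) 95% intervals: 0/6 gives 0% to 46%; 1/6 gives 0.4% to 64%.

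**4. Chance of passing the DLT criterion:** P(X ≤ 1) = (1−p)⁶ + 6p(1−p)⁵.
- p = 0.4: 0.0467 + 0.1866 = 0.233
- p = 0.5: 0.0156 + 0.0938 = 0.109

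The expected number of DLTs in the next 20 is then 20 × 0.4 = 8, or 20 × 0.5 = 10.

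**5. Chance that the pooled 26 then contradict the definition.** With 0 DLTs in the first 6, at least 9 are needed in the 20; with 1, at least 8.
- p = 0.4: (0.0467/0.2333) × 0.404 + (0.1866/0.2333) × 0.584 = 0.081 + 0.467 = 0.548
- p = 0.5: (1/7) × 0.748 + (6/7) × 0.868 = 0.851

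The joint probability of passing at six and then failing at 26 is 0.233 × 0.548 = 12.8% at 40%, and 0.109 × 0.851 = 9.3% at 50%. No DLT-based rule responds in any of these cases.

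**6. An illustrative boundary.** Uniform prior; pause at the smallest count r among n patients for which P(rate > 1/3) > 0.80 under Beta(1+r, 1+n−r). For example, at n = 8, r = 4 gives 0.855 and r = 3 gives 0.650; at n = 24, r = 10 gives 0.822 and r = 9 gives 0.696. The boundary is 4 DLTs by patient 8, 5 by 11, 6 by 13, 7 by 16, 8 by 19, 9 by 21 and 10 by 24. A crossing at patient 26 is left out because accrual is then complete.

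The pause column below comes from an exact patient-by-patient recursion from patient 7, starting from 0 or 1 DLT in 6. The last column uses the formula of step 5.

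| True DLT rate | Pause | 9 or more of 26 |
|---|---|---|
| 20% | 1% | 2% |
| 25% | 4% | 8% |
| 30% | 9% | 20% |
| 40% | 32% | 55% |
| 50% | 64% | 85% |

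Counting a crossing at patient 26 (11 DLTs) as well would give 1%, 4%, 10%, 33% and 67% in the pause column.

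**The case against.** The best case against the point has four parts.

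*Other controls exist.* The 4-of-6 tolerability test can stop a dose that passes on DLTs. Section 5 requires individual holds and reductions. Section 4.1 and the text after Table 4 allow regorafenib to be changed at discretion. Section 8.6 requires reporting of serious events, and section 9.4 provides a medical monitor. This stands in part: it makes 23% and 11% upper bounds on an over-toxic dose reaching expansion. None of these controls counts DLTs in the added patients, however. The tolerability test looks at dose received in cycle 2, with regorafenib judged against the dose at which the patient starts that cycle, so reductions in the first cycle are not counted.

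*A reader might infer that the plan obliges the team to continue at a dose known to be too toxic, or forbids revising the RP2D.* The documents do not support that. The definition in section 4.3 is not expressly limited to six patients, nothing bars a revision, and the section 7.2 tables would make an excess visible. What is absent is a rule that acts on it.

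*Part of the text is unavailable.* A part between sections 8.6.4 and 9.0 was removed before review. If it contains a toxicity rule for Phase II, the point falls. The text just before it concerns notifying the drug supplier of serious events, so this is a caveat and not a rebuttal.

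*The remedy has costs and limits.* This stands. The boundary pauses only about a third of the time at a true rate of 40%. The final check can fail an acceptable dose. The 80% threshold and the uniform prior are mine, not the plan's. A result of 9 or 10 in 26 can fail the final check without ever causing a pause, because the pause asks for strong evidence of excess while the final check compares the observed rate with the definition.

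**Conclusion.** The point holds as a missing decision rule; the plan's calculations are not in error. On the available text, the plan can be followed exactly, complete enrolment, and report an RP2D whose pooled DLT rate is not below 33%. For a dose with a true rate of 40% (50%), the chance of passing the six-patient DLT criterion is at most 23% (11%). Given that it passes, the chance that all 26 patients contradict the definition is 55% (85%).

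These figures assume exactly six patients at the first judgement, independent patients with a constant DLT rate, all 26 evaluable for DLT, and no effect of the tolerability test or of discretionary changes. The pause probabilities also assume that each patient's 4-week window is complete before the next patient enters. With continuing accrual, a pause would come later and spare fewer patients.

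**What to change.** Add a paragraph to sections 4.3 and 7.1 that does the following:

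1. Score DLTs as defined in section 4.5 in every patient treated at the RP2D.
2. Define the DLT-evaluable denominator for Phase II patients. Section 4.5 defines cohort evaluability only for Phase I and response evaluability for Phase II, while section 10.1 counts everyone from first treatment.
3. Apply the plan's one-third limit cumulatively to patients who have completed the 4-week window. Pause enrolment for review by the sponsor and medical monitor at a prespecified boundary, such as the one in the working above. The sponsor may choose another prior or threshold but should show its operating characteristics.
4. At the end, report the pooled DLT rate with its exact confidence interval against the 33% definition. If it is not met, say so, and do not report the dose as the RP2D without qualification.

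This triggers a review and sets no dose or treatment rule. It needs no extra patients or visits, but it does need the denominator definition and running DLT counts. Given at most 1 DLT in 6, the price at true rates of 20%, 25% and 30% is an unneeded pause in about 1%, 4% and 9% of cases, and a failed final check in 2%, 8% and 20%.

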### ***4.4 Experimental Drug Compliance***

Treatment compliance to entinostat and HCQ will be assessed at the end of each cycle. Patients will complete a diary to document their weekly intakes. They will be instructed to return all unused drugs (partially used and empty containers) and their diary at each visit. Site staff will perform accountability of the returned drug and will assess patient compliance. Site staff must ensure that the patient clearly understands the directions for self-medication and follows the schedule.

#### ***4.5 DLT Definition and Escalation Decision Process***

Dose Limiting Toxicities will be defined by toxicity occurring during the first 4 weeks of this study. Any non-hematologic AE of Grade 3 or higher that is judged to be probably treatment-related will be considered a DLT with the exceptions of fatigue; rash attributable to regorafenib; or nausea, vomiting, or diarrhea that has improved to Grade < 1 within 72 hours. Any non-hematologic AE of Grade 4 or higher of any duration that is judged to be probably treatment-related will be considered a DLT except for elevations of lipase and/or amylase in the absence of clinical pancreatitis.

The following hematologic DLT will be considered if any occurs in the first cycle:

- 1) grade 4 neutropenia lasting more than 7 days
- 2) febrile neutropenia (T > 100.4 F in presence of ANC <500)
- 3) platelet count less than 25,000/mm^3
- 4) platelet count less than 50,000/mm^3 with clinically significant hemorrhage

If a DLT is observed in exactly 1 patient in the first cohort of 3, the cohort will be expanded to 6. If a DLT occurs in 2 or more patients per cohort, then the cohort one dose below will be the declared the MTD provided that at least 6 patients have been treated at that level with fewer than one third having DLTs. The rules for dose escalation and cohort size are outlined in Table 3. No intra-patient dose escalation is planned.

***Evaluable Patients:*** Patients will be evaluable for toxicity if they have taken one dose of HCQ and entinostat. Patients who experience a dose-limiting toxicity will be evaluable for the cohort after at least one dose of HCQ and one dose of entinostat. To be considered for evaluability in a Phase I cohort in the absence of dose-limiting toxicity, patients should have completed  $\geq 85\%$  of HCQ doses, and at least 3 of 4 entinostat doses. Phase II patients will be evaluable for response if they have completed 85% of their expected dose of HCQ and at least 3 doses of entinostat in the initial 4 weeks, in the absence of progression. Patients who do not meet these criteria will be replaced. In the unexpected event of excess toxicity at dose level 1, there is provision (Table 3) for a dose reduction of both HCQ and entinostat.

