**Table 4: Phase I: Criteria for Dose Escalation and Cohort Size**

Number of patients with DLT	Rule
0/3 DLT	Escalate
1/3 DLT	Increase cohort to 6 patients
$\geq 2/3$ DLT	De-escalate dose
If the cohort size is increased to 6 patients, the following rules apply	
Number of patients with DLT	Rule
1/6 DLT	Escalate
2/6 DLT	MTD is next lower dose
$\geq 3/6$ DLT	De-escalate dose

The doses of entinostat and HCQ will remain the same for each patient throughout treatment unless there is a need for a dose decrease for toxicity. These DLT decisions are assuming the toxicity is characteristic of entinostat or HCQ.

DLT determination is complex in this three-drug combination, and should the DLT toxicities be more likely associated with regorafenib, a lower dose of regorafenib may be required.

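### The lipase/amylase exemption in Section 4.5 sits only in the grade 4 DLT sentence, so an asymptomatic grade 3 elevation counts as a DLT while grade 4 is either exempt or the exemption is void

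*Combined protocol and SAP*

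**What the plan says.** Section 4.5 gives two rules for non-hematologic DLTs in the first four weeks.

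- The first covers "Any non-hematologic AE of Grade 3 or higher that is judged to be probably treatment-related". It makes such an event a DLT "with the exceptions of fatigue; rash attributable to regorafenib; or nausea, vomiting, or diarrhea", where the gastrointestinal events must have improved within 72 hours. Lipase and amylase are not on this list.
- The second covers probably related events of grade 4 or higher, whatever their duration. Such an event "will be considered a DLT except for elevations of lipase and/or amylase in the absence of clinical pancreatitis".

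The DLT count then drives the dose decisions. "If a DLT is observed in exactly 1 patient in the first cohort of 3, the cohort will be expanded to 6". In Table 4, two DLTs among six patients means "MTD is next lower dose". Section 4.3 adds a further limit: "The RP2D will be defined as a dose in which fewer than 33% of patients have a DLT".

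The text after Table 4 qualifies this. It says "These DLT decisions are assuming the toxicity is characteristic of entinostat or HCQ", and that "should the DLT toxicities be more likely associated with regorafenib, a lower dose of regorafenib may be required".

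**The concern.** The second sentence does useful work only for events that the first one excuses: it brings grade 4 fatigue, rash and gastrointestinal events back in as DLTs. Lipase and amylase were never excused in the first sentence, so an exemption placed only in the second does not fit.

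The likely purpose is that enzyme elevations without pancreatitis should not drive dose decisions at either grade. The text does not say so. An investigator applying it literally would count the milder event and might not count the more severe one.

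One counted event turns 0/3 into 1/3 and adds three patients to the cohort. A second DLT among six stops escalation and moves the MTD down a level. It also breaches the RP2D limit, because 2/6 = 33.3% is not below 33%. The event is foreseeable: every patient receives regorafenib, and Section 2.5 reports grade 3-4 lipase elevation with that drug.

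**Working it through.** **Reading the two sentences together.** For a probably related elevation without clinical pancreatitis:

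| Grade | Grade 3 or higher sentence | Grade 4 or higher sentence | Result |
|---|---|---|---|
| 3 | DLT, no exception applies | does not apply | DLT |
| 4, second sentence governs | set aside | exempt | not a DLT, although grade 3 is |
| 4, both sentences apply | DLT, no exception applies | exempt | DLT, and the exemption has no effect |

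Nothing elsewhere in the document extends the exemption to grade 3.

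**Reproducing the plan's figures.** Under Section 7.1.1 the dose is escalated after 0/3 DLTs, or after 1/3 followed by 0/3. With DLT probability p per patient:

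P(escalate) = (1−p)³ + 3p(1−p)² × (1−p)³

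For p = 0.1 to 0.8 in steps of 0.1 this gives 0.906, 0.709, 0.494, 0.309, 0.172, 0.082, 0.032 and 0.009. All eight rows of Table 11 are reproduced.

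**Sizing the effect.** Inputs:

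- b, the rate of other DLTs: 10% and 20%, two rows of Table 11.
- r, the rate of lipase/amylase events detected and counted in cycle 1. The documents do not give it. Their only figure is 6% grade 3-4 lipase elevation on regorafenib alone in the second phase III trial described in Section 2.5, taken here as a rate over that whole trial. I assume a quarter to a half of it: 0.25 × 6% = 1.5% and 0.5 × 6% = 3%.
- Independence of the two sources, so p = 1 − (1−b)(1−r).

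| b | r | p | P(escalate) | Drop, points |
|---|---|---|---|---|
| 0.10 | 0 | 0.100 | 0.906 | – |
| 0.10 | 0.015 | 0.1135 | 0.883 | 2.3 |
| 0.10 | 0.03 | 0.127 | 0.859 | 4.8 |
| 0.10 | 0.06 | 0.154 | 0.806 | 10.0 |
| 0.20 | 0 | 0.200 | 0.709 | – |
| 0.20 | 0.015 | 0.212 | 0.683 | 2.6 |
| 0.20 | 0.03 | 0.224 | 0.656 | 5.2 |
| 0.20 | 0.06 | 0.248 | 0.604 | 10.4 |

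The 6% rows are a ceiling. They assume that every patient is tested, every event falls in the first four weeks and is judged probably related, and none is set aside as a regorafenib effect.

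**How often it would arise.** The chance of at least one counted event in a cohort of three is 1 − 0.985³ = 4.4% to 1 − 0.97³ = 8.7%. Over the 12 to 24 Phase I patients in Section 7.3, the expected number is 12 × 0.015 = 0.18 to 24 × 0.03 = 0.72.

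**What the figures compare.** They set full exemption against counting every grade 3-4 elevation. If grade 4 events are exempt, only the grade 3 share counts and the drop is smaller. The documents do not split the 6% by grade, so the ambiguous grade 4 part cannot be sized.

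**The case against.** The strongest reply is that the event would rarely reach the hydroxychloroquine/entinostat decision.

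- The only documented lipase rate belongs to regorafenib. Neither enzyme is in the entinostat table (Table 9) or the hydroxychloroquine table (Table 10).
- The text after Table 4 assumes toxicity typical of those two drugs. Section 4.1 keeps regorafenib dose changes out of the MTD, and Section 5.1 handles grade 3-4 regorafenib reactions by interruption and reduction.
- Lipase and amylase are not in the scheduled chemistry panel (Appendix A, footnote 6). A laboratory value must also first qualify as an adverse event under Sections 8.1.1 and 8.3.
- At grade 4 a specific exemption would normally prevail over a general rule, and a sensible investigator would probably infer the intent. Counting grade 3 could also be defended as deliberate caution in a three-drug combination.

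Most of this stands as a limit on size. It does not repair the definition. Section 4.5 requires only that the event be related to treatment, without naming a drug. The text after Table 4 says a lower regorafenib dose may be needed, not that the event is not a DLT. Sections 4.1 and 5.1 concern dosing rather than classification. Infrequent testing makes the question rarer but does not answer it once a high value is found. And if the specific exemption prevails at grade 4, the inverted ordering of grades remains. Deliberate caution at grade 3 is hard to reconcile with an exemption at grade 4.

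**Conclusion.** The concern holds, as a minor point. The two sentences are inconsistent: grade 3 has one literal answer, a DLT; grade 4 has two possible answers, and neither is likely to be intended.

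The error can only add DLTs relative to exemption at both grades, so it cannot push the dose up. Its cost is extra patients, time, or an MTD one level too low. On the assumed 1.5% to 3% the loss is about 2 to 5 percentage points per escalation decision, with fewer than one counted event expected in the whole of Phase I. If these events are treated as regorafenib toxicity and kept out of the decision, the loss is nearer zero. The assumed rates illustrate scale and are not estimates. Table 11 is correct as printed, and the Phase II sample size and power are unaffected.

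**What to change.** Add lipase and/or amylase elevation without clinical pancreatitis to the exceptions in the grade 3 or higher sentence of Section 4.5, and keep the exemption in the grade 4 or higher sentence. It is needed in both places, because the second sentence otherwise brings grade 4 elevations back in. Leave the rest alone, so that grade 4 fatigue, rash and gastrointestinal events still count as DLTs. The sponsor should first confirm that exemption at both grades is the intent.

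The cost is one phrase and a protocol amendment submitted to the EC/IRB under Section 11.0, with no added test, visit or patient. The downside is small but real: asymptomatic grade 3 elevations would no longer count as DLTs.

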### ***4.2 Phase I Dose Escalation of Hydroxychloroquine and Entinostat***

We expect that the full doses of each drug will be well-tolerated based on previous studies. Patients will begin treatment with weekly oral entinostat and daily oral HCQ given in divided doses, per Table 3 below. The starting phase I total daily dose for HCQ is 600 mg, based on our previous Phase I trials. Weekly dosing of entinostat has been established as the best balance between toxicity due to accumulation and drug pharmacodynamics. Entinostat is currently undergoing study at a dose of 5mg weekly in a phase III trial in breast cancer, and 5mg weekly will be the target dose for this study. Given the potential for overlapping toxicities in this combination, an initial dose of 3 mg will be used, with subsequent escalation.

Three patients will be treated at the starting doses, with escalation to an entinostat dose of 5mg at dose level 2 followed by dose escalation of HCQ to 1200 mg/daily at dose level 3, with expansion to a total of 6 patients once safety has been established. Dose levels 2A and 2B will not be used during the dose escalation phase, they will be used only if de-escalation from dose level 3 is required. Toxicity attributable to hydroxychloroquine is not expected given its excellent tolerability in multiple phase II studies with combination chemotherapy using 1200 mg per day. In the event that dose level 3 exceeds the MTD (as described below), provision is made for stepwise dose de-escalation by 200 mg to dose levels 2B (1000 mg total daily dose HCQ) then 2A (800 mg total daily dose HCQ).

Before accrual to the next dose level may begin, all patients in the first cohort must complete the first 4 weeks of treatment, permitting toxicities to be assessed. The target DLT rate is  $\leq 33\%$ . The MTD will be defined as a) the dose producing DLT in 1 out of 6 patients, or b) the dose level below the dose which produced DLT in  $\geq 2$  out of 3 patients, or in  $\geq 2$  out of 6 patients. The rules for dose escalation and cohort size are outlined in Table 3. No intra-patient dose escalation is planned.

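### The hematologic DLT list in section 4.5 covers only neutrophils and platelets, so an isolated, treatment-related grade 4-5 anemia or hemolysis never enters the Table 4 count

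*Combined protocol and SAP*

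**What the plan says.** Section 4.5 has two general grade rules, and both exclude hematologic events: "Any non-hematologic AE of Grade 3 or higher that is judged to be probably treatment-related will be considered a DLT", with listed exceptions, and "Any non-hematologic AE of Grade 4 or higher of any duration that is judged to be probably treatment-related will be considered a DLT", except for lipase or amylase elevations without clinical pancreatitis.

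Hematologic events have a separate route: "The following hematologic DLT will be considered if any occurs in the first cycle". Four items follow: grade 4 neutropenia beyond 7 days, febrile neutropenia, platelets below 25,000, and platelets below 50,000 with significant bleeding. There is no hemoglobin, anemia or hemolysis item, no general grade 4 hematologic item and no grade 5 clause.

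The same section sets evaluability. Without a DLT, a phase I patient needs at least 85% of HCQ doses and 3 of 4 entinostat doses; "Patients who do not meet these criteria will be replaced". With a DLT the bar is lower: "Patients who experience a dose-limiting toxicity will be evaluable for the cohort after at least one dose of HCQ and one dose of entinostat".

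Escalation uses the DLT count alone. Section 7.1.1 states "If 0/3 patients experience DLT, then the dose will be escalated", and the Table 4 action for 1/3 is "Increase cohort to 6 patients". Sections 4.2 and 7.1.1 and Table 4 use the term DLT without widening it.

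**The concern.** Red-cell toxicity is foreseen for both added drugs. Section 2.7 reports anemia in 26% of patients (all grades) in the first entinostat phase I study. The hematologic row of Table 10 lists aplastic anemia for HCQ, and hemolysis in patients with the enzyme deficiency. Yet a life-threatening or fatal red-cell event attributed to treatment can fall outside both DLT routes, while nearly any non-hematologic event of the same grade and attribution would count.

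The decisions at stake are the steps from entinostat 3 to 5 mg (level 1 to 2) and from HCQ 600 to 1200 mg (level 2 to 3). With three patients per decision, one event changes the action.

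**Working it through.** **The plan's own figures.** Under section 7.1.1, escalation follows 0/3 DLTs, or 1/3 followed by 0/3. For a true DLT rate p:

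P(escalate) = (1−p)³ + 3p(1−p)² × (1−p)³

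For p = 0.1 to 0.8 this gives 0.906, 0.709, 0.494, 0.309, 0.172, 0.082, 0.032 and 0.009. All eight Table 11 values are reproduced to two decimals. Table 11 is right for DLTs as section 4.5 defines them, and no change to it is claimed.

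**How cycle 1 red-cell events are classified**, when judged probably related:

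| Event | Status under 4.5 |
|---|---|
| Brings a probably related grade 3+ non-hematologic AE (such as raised bilirubin or creatinine, dyspnea, bleeding) | Counts, unless a listed exception applies |
| Aplastic anemia with low neutrophils or platelets | May meet a listed item |
| Grade 4-5 anemia or hemolysis with neither | Not a DLT |

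Only the last row is at issue.

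**What happens to that patient.** HCQ twice daily for 28 days is 56 doses. 85% of 56 is 47.6, so 48 doses are needed and 8 (4 days) may be missed.

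- HCQ held on days 25-28: 24/28 = 85.7%. With 3 of 4 entinostat doses taken, the patient is evaluable and scored DLT-free.
- HCQ held on days 24-28: 23/28 = 82.1%. The patient is replaced, and escalation waits for the replacement, since section 4.2 says "Before accrual to the next dose level may begin, all patients in the first cohort must complete the first 4 weeks of treatment".

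On either path the event does not enter the count.

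**Effect on Table 4.** Take one such event in the first three patients and no listed DLT in the three evaluable patients. As written the count is 0/3: escalate. If the event were counted it would be 1/3: expand to 6.

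**How often.** The documents give no rate for the combination. Section 2.7 says the only grade 4 event among 23 patients was leukopenia and neutropenia in one patient, which implies 0/23 grade 4 anemia on entinostat alone. The one-sided 95% upper bound for 0/23 is 1 − 0.05^(1/23) = 0.122. This is a small-sample ceiling, not an estimate, and it refers to any grade 4 anemia, not only the isolated, related, cycle 1 event. The 1%, 2% and 5% rates below are assumptions.

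For three patients, P(X≥1) = 1 − (1−p)³ and P(X≥2) = 3p²(1−p) + p³:

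| Per-patient rate p | At least one of 3 | Two or more of 3 |
|---|---|---|
| 1% | 3.0% | 0.03% |
| 2% | 5.9% | 0.12% |
| 5% | 14.3% | 0.73% |
| 12.2% (ceiling) | 32.3% | 4.1% |

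**The case against.** The strongest reply is that the gap is nearly empty.

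- **Rarity.** Entry requires hemoglobin of at least 9 g/dL (3.1.12). Table 10 ties hemolysis to an enzyme deficiency that is excluded when known (3.2.7). A fatal anemia without a related cardiac, hypoxic or bleeding event is hard to picture. Table 9 also lists red-cell transfusion as a procedure-type event, which might qualify depending on coding and grade. All this stands and is why the priority is low. However, Appendix A schedules no G6PD test, and a transfusion code is not a dependable route.
- **The DLT-free path is narrow.** Section 5.3.1 holds HCQ for grade 3 or higher events at least possibly related to it. The only routine count between day 1 and the start of cycle 2 is on day 15, so an HCQ-attributed event found then usually ends in replacement. That is fair, but replacement also removes the event from the count. Where only entinostat is blamed, no tabulated hold applies: Table 6 is triggered by neutropenia and thrombocytopenia, and Table 5 is non-hematologic.
- **Other safeguards.** SAEs are reported within 24 hours, and there is a medical monitor. Section 7.1.1 tabulates toxicity by dose level. Section 4.3 replaces patients in the MTD cohort only when they leave for reasons other than toxicity, so severe anemia could weigh against tolerability there. These give oversight, but none makes the event a DLT, and the section 4.3 check applies only at the MTD.
- **A deliberate choice.** The entinostat dose-modification table has the same neutrophil and platelet focus, and the first phase I study saw more neutropenia (74%) and thrombocytopenia (61%) than anemia. This supports leaving grade 3 anemia off the list. It does not justify leaving out a life-threatening or fatal related event.
- **Unsourced rates, modest effect.** The assumed rates are illustrative, and one counted event only adds three patients; if none of them has a DLT, escalation proceeds. Both points are correct. The finding rests on the text, not on the rates.

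**Conclusion.** The concern holds as a narrow gap in the DLT definition. A probably related, isolated grade 4-5 anemia or hemolysis in cycle 1 is outside both routes in section 4.5, and one such event in the first three patients changes the Table 4 action from expansion to escalation.

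The reading depends only on the current text. The frequency depends on assumed rates and independence between patients. No severe-anemia signal appears in the documents, so the expected effect is small. This is an inexpensive, low-priority improvement to a safety rule, not the correction of a known bias.

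**What to change.** Add one item to the hematologic list in section 4.5: *any grade 4 or higher anemia or hemolysis, or any other grade 5 hematologic event, judged to be probably treatment-related.*

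Add a clause noting that these patients fall under the existing evaluability sentence for DLT patients (one dose each of HCQ and entinostat), so that the 85% rule does not replace them.

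The four existing hematologic items carry no attribution test, so the new item would be the only one on that list that does. The threshold is the one section 4.5 already uses in its two non-hematologic rules.

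The cost is one list item and one clause. No new test is needed, because section 4.8 already schedules blood counts every two weeks until week 8. A few more events may count as DLTs, making escalation slightly less likely.
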